9.6 Statistical criteria and definition of endpoints

9.6.1 Response rate (main endpoint)

The primary analysis will evaluate complete response rate at 3 months from randomisation in an intent-to-treat (ITT) population containing all randomized patients. A valid response has to be measured at month 3 plus and minus 10 days; in case of more than one measurement in this period, the best response will be taken. Death before 3 months will be considered a failure (i.e. no response). We expect a very limited number of cases alive at 3 months and non-evaluable, or withdrawals before 3 months; these cases will be excluded from the primary analysis, and sensitivity analyses will be performed to check the validity of conclusions.

9.6.2 Time to first response

Time to first response is defined as time from randomisation until the first assessment of partial or complete response confirmed in at least 3 consecutive determinations; it will be described by a cumulative incidence curve, considering as competing event any of the following events occurring prior to response achievement: death for any cause, stem cell transplant (SCT), any new specific AA treatment and clonal evolution (as defined in 9.5) (observations will be censored for patients event-free at last follow-up).

9.6.3 Time to best response

Time to best response is defined as time from randomisation until the date of assessment of the best response (partial or complete) confirmed in at least 3 consecutive determinations; it will be described by a cumulative incidence curve, considering as competing event any of the following events occurring prior to response achievement: death for any cause, stem cell transplant (SCT), any new specific AA treatment and clonal evolution (as defined in 9.5) (observations will be censored for patients event-free at last follow-up).

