5.2 Secondary Endpoints

1. Time to first hematological response (complete or partial) described by a cumulative incidence curve (see paragraph 9.6)
2. Time to best hematological response, described by a cumulative incidence curve (see paragraph 9.6)
3. Time to complete response (see paragraph 9.6)
4. Rates of hematological response (overall, complete, partial) at 6, 12, 18 and 24 months
5. Overall survival (OS) probability; OS is defined as time from randomisation to death, or last follow-up for patients alive
6. Event-free survival (EFS) probability; EFS is defined as time from randomisation to either relapse, death, treatment failure or clonal evolution (whichever occurs first), or last follow-up for patients alive in response
7. Cumulative incidence of relapse, from first hematological response (complete or partial) (see paragraph 9.6)
8. Cumulative incidence of clonal evolution (as defined below, see 9.5): AML, MDS or karyotypic abnormalities (see paragraph 9.6)
9. Cumulative incidence of PNH population occurrence and clinical hemolytic PNH occurrence (see paragraph 9.6)
10. Cumulative incidence of discontinuation of immunosuppressive therapy
11. Rate of CsA-independent hematological response at 24 months
12. Need for transfusions (packed red cell units and platelet units) and number of transfusions required from treatment.
13. Need for any supportive care, including hospitalization
14. Quality of life (as assessed by the validated EORTC QLQ-C30 questionnaire)(changes over time and differences between treatment arms)
15. Safety and tolerability of the investigational treatment, including SAE

6. Patient Selection and Withdrawal

All patients must meet all of the inclusion criteria and none of the exclusion criteria listed below. Protocol waivers are not acceptable in this trial.

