7.2.3 Duration of Patient Participation

Patients will be included in the trial following informed consent. Following registration patient will start hATG within 7 days. Patients have to be randomised at, or the day before, start of hATG treatment.

Patients will remain on the trial for 2 years (for treatment and subsequent follow up); the duration of the treatment with the IMP will be initially 3 or 6 months (depending on hematological response). However, given that re-introduction of the IMP is allowed for 6 additional months, the treatment duration may be extended up to 18 months from enrolment. Per protocol, eltrombopag (the investigational agents) will be administered for a maximum period of 12 months: maximum 6 months at enrolment, plus additional maximum 6 months in

case of early relapse. As long-term effects of investigational treatments are an objective of the study, the follow-up of patients will cover a minimum of 24 months from initial randomisation. The long term follow up of the patients will be conducted outside of the protocol and will be extended up to 10 years from treatment, through the EBMT official database (updated EBMT Registry Database).

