12.3 Statistical Methods

The primary analysis will evaluate the complete response rate at 3 months from randomisation in an ITT population containing all randomized patients. Response is defined in section 9.6.1. We expect a very limited number of cases alive at 3 months and non-evaluable, or withdrawals before 3 months; these cases will be excluded from the primary analysis, and sensitivity analyses will be performed to check the validity of conclusions.

The null hypothesis of no difference in CR rate at 3 months between the arms will be tested against the alternative of a difference in CR rate by assessing the Mantel Haenszel pooled Odds Ratio for arm yielded by a model stratified for center, age and disease severity (strata defined in 7.1 and 12.2; alpha level of .05).

The analysis of survival-like endpoints (OS, EFS; defined in 9.6) will be done by Kaplan-Meier curves and stratified Log-Rank test and Cox regression (provided the absence of relevant deviations from the assumption of proportionality of hazards).

The analysis of time-to-event endpoints with competing risks (Time to first response, Time to best response, Time to CR, RI, Clonal evolution, PNH and immunosuppression discontinuation; defined in 9.6) will be done by crude cumulative incidence curves, Gray test, and Cox regression for cause-specific hazards (provided the absence of relevant deviations from the assumption of proportionality).

Other secondary endpoints (CsA-independent hematological response at 24 months, Need for transfusions, Need for any supportive care including hospitalization, Safety and tolerability) will be described by standard summary statistics (frequency tables for categorical variables, mean with standard deviations and quantiles for continuous variables).

QoL data will be analyzed by mixed models, assessing changes over time and differences between treatment arms.

Exploratory analyses of outcomes will also address the impact of other relevant predictive factors, which include:

- The presence of a PNH population
- The presence of HLA dr 15
- Pre-treatment absolute reticulocyte count
- Pre-treatment absolute lymphocyte count
- ANC at 1 month (time-dependent covariate)
- Platelets and absolute reticulocyte count at 3 months (time-dependent covariate)

For all tests, the alpha level will be .05. All analyses will be performed in SPSS and / or R.

Further details will be specified in a separate Statistical Analysis Plan (SAP).

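### Time to best response is dated by the patient's later course and moves later when a partial response deepens, so the planned Gray and Cox comparison of arms has no clear direction

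*Protocol*

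**What the plan says.** Protocol section 5.2 lists, as secondary endpoint 2, "Time to best hematological response, described by a cumulative incidence curve". Section 9.6.3 dates the event as "time from randomisation until the date of assessment of the best response (partial or complete) confirmed in at least 3 consecutive determinations". Death, transplant, new treatment for aplastic anaemia and clonal evolution compete only if they come before response. No month is set by which the best response must be reached.

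Section 12.3 places this endpoint in a group with "Time to first response, Time to best response, Time to CR, RI" and others, whose analysis "will be done by crude cumulative incidence curves, Gray test, and Cox regression for cause-specific hazards". It adds: "For all tests, the alpha level will be .05". Section 7.2.3 says that "the follow-up of patients will cover a minimum of 24 months from initial randomisation".

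Time to first response (9.6.2) and time to complete response (9.6.4) are separate endpoints. Response rates at 6, 12, 18 and 24 months are secondary endpoint 4.

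**The concern.** Take two patients who both reach PR at month 3. One stays in PR, and the event is dated at month 3. The other improves to CR at month 12, and the event is dated at month 12, so this patient counts as event-free for nine months spent in response. Which date applies cannot be known at month 3.

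The Gray test and the Cox model treat an earlier event as the better outcome, so the patient who did better is scored as slower. The curve ends at the proportion with any response, so the CR earns nothing at the plateau to offset the delay. A partial responder who leaves the study before a CR would have come is also scored early.

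Section 2.1 gives improved quality of response as the trial's rationale. If eltrombopag deepens responses, this test counts that against it. A formal p-value at 0.05 would then be attached to a quantity for which neither faster nor slower has a fixed meaning.

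**Working it through.** **The plan's own figures.** The protocol gives none for this endpoint. Its sample size is for the primary endpoint and reproduces. With 7% v 21%, two-sided 0.05, 80% power and pooled variance, n = [1.960·√(2·0.14·0.86) + 0.842·√(0.07·0.93 + 0.21·0.79)]² / 0.14² = 95.2, so 96 per arm. This point does not change it.

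**Arithmetic from the definition.**
- Input: response of 62% at 3 months and 68% at 6 months on horse ATG plus ciclosporin (section 2, Background), taken as equal in both arms.
- Assumption: a share d of responders deepens from PR to CR at month 12.
- Formula: before month 12 the incidence of best response is F(t)·(1 − d); from month 12 it is 68%.

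| d | Month 3 | Month 6 | Month 12 |
|---|---|---|---|
| 20% | 0.62·0.8 = 49.6% | 0.68·0.8 = 54.4% | 68% |
| 40% | 0.62·0.6 = 37.2% | 0.68·0.6 = 40.8% | 68% |
| 60% | 0.62·0.4 = 24.8% | 0.68·0.4 = 27.2% | 68% |

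With identical first-response times, the arm with more CRs has the lower curve until month 12 and the same plateau. That direction follows from the definition; only the size depends on d.

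**Adding the trial's own hypothesis.** Section 12.1 assumes 7% v 21% CR at 3 months. Those patients have early best-response events. Let d apply to the remaining responders. At month 6:
- Control, d = 20%: 7 + (68 − 7)·0.8 = 55.8%.
- Eltrombopag, d = 20%: 21 + (68 − 21)·0.8 = 58.6%.
- Eltrombopag, d = 40%: 21 + 47·0.6 = 49.2%.
- Eltrombopag, d = 60%: 21 + 47·0.4 = 39.8%.

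**Simulated tests.** 100 per arm; first response uniform over 1.5–6 months; upgrades 3–12 months later; non-responders kept to 24 months; no competing events, so the log-rank test stands in for Gray's. Early CRs, where included, are dated at 1.5–3 months. All these timings and the upgrade shares are assumptions.

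| Responding, control v eltrombopag | CR at 3 months | Upgrading | Significant for control | Significant for eltrombopag |
|---|---|---|---|---|
| 68% v 68% | none | 20% v 60% | 23–28% | about 0–0.1% |
| 68% v 68% | none | 20% v 40% | about 10% | about 0.5% |
| 68% v 68% | 7% v 21% | 20% v 60% | 6–7% | about 1% |
| 68% v 68% | 7% v 21% | 20% v 40% | 2–2.5% | 2–3% |
| 68% v 68% | 7% v 21% | 20% v 20% | 1.1% | 7.2% |
| 68% v 75% | 7% v 21% | 20% v 40% | 0.3% | 15.7% |
| 68% v 80% | 7% v 21% | 20% v 60% | 0.4% | 17.1% |

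Ranges are the spread over repeated simulations.

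**Against the neighbouring endpoints.** A second model has no early CR, first response at 3, 6, 9 or 12 months in 60/25/10/5% of responders, and upgrades 3–12 months later. Hazard ratios above 1 favour eltrombopag.
- 68% in both arms, 20% v 20% upgrading: best response 1.00, significant in 2.3% for control and 3.0% for eltrombopag. The test holds its level when nothing differs.
- 68% in both arms, 20% v 60%: first response 1.00, CR 3.37 (significant in 99.5%), best response 0.82 (significant for control in 16.9%).
- 68% v 75%, 20% v 60%: first response 1.24, best response 0.98. The benefit is masked.
- 68% v 80%, 20% v 60%: first response 1.48 (significant in 46.8%), best response 1.11 (significant for eltrombopag in 8.8%). The benefit is diluted.

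**The case against.** The strongest reply is that a reversal needs particular conditions. The trial is powered on early CR, and an early CR is an early best-response event that favours eltrombopag. Once 7% v 21% is included, the reversal is small, absent or goes the other way. Section 8.1.1.2 ends the initial eltrombopag course at 3 months in CR and by 6 months otherwise, and nothing in the protocol supports a threefold difference in late upgrading. This stands, and it limits the size that can be claimed.

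A reader might infer that this endpoint is likely to show significant harm from eltrombopag, or that the trial's conclusion is at risk. The documents do not support that. Time to first response and time to CR sit beside it, and a slower best response with a faster CR would be read as deepening.

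Dependence on follow-up is also minor: everyone is to be followed for at least 24 months, and section 6.3 keeps patients who stop treatment in follow-up. It would matter mainly if departures differed between arms.

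Lastly, section 9.6.3 speaks only of describing the curve, the test comes from a grouped list, and section 12.3 leaves further detail to a SAP. But section 12.3 names this endpoint and these tests, and nothing in the protocol qualifies how the comparison is to be read. Sound neighbouring endpoints make the test dispensable; they do not make it interpretable.

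**Conclusion.** The point holds as a fault in one stated secondary analysis. By definition the event date depends on the patient's future, deepening moves it later, and the plateau does not separate CR from PR. A test that reads earlier as better therefore has no clear direction and can mask, dilute or in some settings reverse a real benefit.

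The size is uncertain because the protocol gives no upgrade shares or delays. About 23–28% of trials significant for control is an unfavourable case: equal overall response, no early CR and 20% v 60% upgrading. Under the protocol's own early-CR hypothesis the figure is about 6–7%. The test is about neutral at 20% v 40% upgrading and favours eltrombopag when overall response also rises. The primary endpoint and sample size are untouched.

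**What to change.** In section 12.3, take time to best response out of the group analysed by Gray test and Cox regression. In section 9.6.3, state that it is reported descriptively only. Keep time to first response and time to CR as the tested times. If an arm comparison of best response is wanted, compare it as a category (no response, PR or CR) reached by a fixed month such as 6 or 24. This supplements the response rates already in secondary endpoint 4 and is close to them, so it is optional.

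The cost is wording in two sections and the loss of one secondary formal test. The data and visits stay the same.

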9.6.4 Time to complete response

Time to complete response is defined as time from randomisation until the date of achievement of complete response confirmed in at least 3 consecutive determinations; it will be described by a cumulative incidence curve, considering as competing event any of the following events occurring prior to response achievement: death for any cause, stem cell transplant (SCT), any new specific AA treatment and clonal evolution (as defined in 9.5).

9.6.5 Overall survival (OS)

Overall survival is defined as time from randomisation until death; observations will be censored for patient alive at last follow-up.

9.6.6 Event-free survival (EFS)

Event-free survival is defined as time from randomisation to either relapse, death, treatment failure or clonal evolution (whichever occurs first), censoring observations at last follow-up for patients alive event-free.

9.6.7 Relapse incidence (RI)

Time to relapse is defined as time from first hematological response (complete or partial) until relapse, death without prior relapse, SCT and clonal evolution (as defined in 9.5) will be considered competing events.

9.6.8 Clonal evolution, PNH and immunosuppression discontinuation

Incidence and time to clonal evolution will be evaluated in a competing risks framework, considering death and SCT before clonal evolution as competing events.

Incidence and time to PNH will be evaluated in a competing risks framework, considering death and SCT before PNH as competing events.

Incidence and time to discontinuation of immunosuppressive therapy will be evaluated in a competing risks framework, considering death and SCT before discontinuation of IS as competing events.

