	
Secondary:
 
 1. Time to first hematological response (complete or partial) described by a cumulative incidence curve (see paragraph 9.6) 2. Time to best hematological response, described by a cumulative incidence curve (see paragraph 9.6) 3. Time to complete response (see paragraph 9.6) 4. Rates of hematological response (overall, complete, partial) at 6, 12, 18 and 24 months 5. Overall survival (OS) probability; OS is defined as time from randomisation to death, or last follow-up for patients alive 6. Event-free survival (EFS) probability; EFS is defined as time from randomisation to either relapse, death, treatment failure or clonal evolution (whichever occurs first), or last follow-up for patients alive in response 7. Cumulative incidence of relapse, from first hematological response (complete or partial) (see paragraph 9.6) 8. Cumulative incidence of clonal evolution (as defined below, see 9.5): AML, MDS or karyotypic abnormalities (see paragraph 9.6) 9. Cumulative incidence of PNH population occurrence and clinical hemolytic PNH occurrence (see paragraph 9.6) 10. Cumulative incidence of discontinuation of maintenance immunosuppressive therapy (CsA) 11. Rate of CsA-independent hematological response at 24 months 12. Need for transfusions (packed red cell units and platelet units) and number of transfusions required from treatment. 13. Need for any supportive care, including hospitalization 14. Quality of life (as assessed by the validated EORTC QLQ-C30 questionnaire)(changes over time and differences between treatment arms) 15. Safety and tolerability of the investigational treatment, eltrombopag, and ATGAM including SAE
Number of patients required	200 (100 patients in each arm)

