6.3 Early withdrawal of a patient / patient drop-out from the trial treatment

The site investigator should withdraw a patient from the trial treatment whenever continued participation is no longer in the patient's best interests. In particular, change of protocol treatment is expected in case of treatment failure (as defined in paragraph 9.4) for those patients who are eligible for second-line treatment (i.e., transplantation or second course of immunosuppression).

In addition reasons for discontinuing treatment may include:

1. the occurrence of a serious adverse event:
2. unrelated medical illness or clinical conditions representing a potential risk - at judge of the investigator, including pregnancy.
3. significant protocol violation or non-compliance (including unmotivated refusal by the subject for prescribe study procedures and post-treatment follow up).
4. a patient's own request to end treatment.

²Eltrombopag was not teratogenic when studied in pregnant rats and rabbits but caused a low incidence of cervical ribs (a fetal variation) and reduced fetal body weight at doses that were maternally toxic. There are no adequate and well-controlled studies of eltrombopag in pregnant women. The effect of eltrombopag on human pregnancy is unknown. Therefore women of childbearing potential must agree to use adequate contraception prior to (hormonal or barrier method of birth control; abstinence) and for the duration of study participation. If a woman becomes pregnant or suspects she is pregnant while on study, her treating physician should be informed immediately.

³ATGAM was not teratogenic when studied in rats or monkeys at a dose up to 20 mg/kg. However, 20 mg/kg/day ATGAM for 16 days during organogenesis in cynomolgus monkeys was fetotoxic. No fetal or maternal toxicity was seen with 10 mg/kg/day ATGAM administered for 16 days during organogenesis. There are no adequate and well-controlled studies in pregnant women. It is also not known whether ATGAM can cause fetal harm when administered to a pregnant woman or can affect reproduction capacity.

If a patient is withdrawn from treatment for any reason, he or she remains in the trial and is followed through the regular follow ups for the normal duration of the described participation as per protocol, unless the patient specifically withdraws consent from the trial.

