8.6.3 Cyclosporin A dose adjustment

The drug-drug interaction potential between eltrombopag and CsA is unknown. Both CsA and eltrombopag are inhibitors of OATP and BCRP drug transporters, and eltrombopag is a substrate of BCRP in vitro. It is not known if the combination will result in any PK changes to either drug.

Patients will be monitored for signs of CsA toxicity during the study, and therapeutic drug monitoring can be instituted as required. Cyclosporin A levels should be adjusted to maintain concentration of 200-400ng/mL (using a polyclonal assay) or 150-250 ng/mL (using a monoclonal assay). Dose may be decreased at any time in case of CsA-related adverse effects, such as hypertension, increased serum creatinine, peripheral neuropathy; dose reduction should be targeted to the higher dose effective in controlling abnormalities. In case of persisting and clinically significant abnormalities, the investigator may decide to discontinue the drug.

Rheumatoid arthritis patients with abnormal renal function, uncontrolled hypertension, or malignancies should not receive Cyclosporine A.

Psoriasis patients who are treated with Neoral should not receive concomitant PUVA or UVB therapy, methotrexate or other immunosuppressive agents, coal tar or radiation therapy. Psoriasis patients with abnormal renal function, uncontrolled hypertension, or malignancies should not receive Cyclosporine A.

Nephrotoxicity was seen early after transplantation and was characterized by a rapidly rising BUN and creatinine. Since these events are similar to rejection episodes, care must be taken to differentiate between them. This form of nephrotoxicity is usually responsive to cyclosporine A dosage reduction.

Due to the potential for additive or synergistic impairment of renal function, caution should be exercised when co-administering Cyclosporine A with other drugs that may impair renal function.

Renal and liver functions will be assessed repeatedly by measurement of serum creatinine,

serum bilirubin, and liver enzymes.

Eltrombopag dosing may be interrupted based on platelet count, reducing the potential impact of an underlying PK interaction (see paragraph 8.6.1: Eltrombopag stopping rules).

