8.11.1 Open-label eltrombopag treatment

The following patients will be eligible for open-label eltrombopag treatment:

- Patients randomized in the control arm (ATGAM + CsA without eltrombopag) who:
 - Show no hematological response at 6 months;
 - Do not demonstrate any clonal evolution at 6 months (as confirmed by bone marrow karyotyping);

(See section 12 for related methodological issues)

All these patients are eligible to receive a course of eltrombopag; at judge of the investigator, eltrombopag will be offered as either:

- Single agent treatment;
- Eltrombopag associated with second course of immunosuppression (without any restriction concerning the anti-lymphocyte agent).

Eltrombopag treatment will be started at the same dose of 150 mg/day, and will be continued for 3 months in case of complete response at 3 months from re-introduction, or up to 6 months. After these 6 months of treatment, eltrombopag will be discontinued in any case independently from hematological response; the patients will continue the follow up, as prescribed per protocol (see paragraph 7.2).

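### The cyclosporine-discontinuation endpoint counts stops after failure or for toxicity the same as withdrawal in stable response, so its between-arm test can mislead about weaning

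*Protocol*

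**What the plan says.** Protocol 9.6.8 fixes both the event and what competes with it. The event is set out as follows: "Incidence and time to discontinuation of immunosuppressive therapy will be evaluated in a competing risks framework". The list of what competes is closed and names two items only: "considering death and SCT before discontinuation of IS as competing events". Section 5.2, item 10, gives the endpoint as "Cumulative incidence of discontinuation of immunosuppressive therapy", again unqualified, and objective 10 in 4.2 adds nothing. The synopsis (1.1) reads "Cumulative incidence of discontinuation of maintenance immunosuppressive therapy (CsA"), which names the drug and calls it maintenance but sets no condition on reason or response.

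Section 12.3 compares this endpoint between arms by cumulative incidence curves, Gray test and cause-specific Cox regression, at alpha .05.

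Elsewhere the protocol describes three routes to stopping CsA:
- **Planned withdrawal (8.12):** tapering begins after one year in stable response, at about 10% per month, with at least 18 months on CsA before withdrawal.
- **Toxicity (8.6.3):** "In case of persisting and clinically significant abnormalities, the investigator may decide to discontinue the drug".
- **Failure (6.3):** "change of protocol treatment is expected in case of treatment failure (as defined in paragraph 9.4") in patients eligible for second-line treatment. Section 8.11 leaves that treatment to the investigator and does not limit it to transplant.

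**The concern.** The three routes carry opposite meanings. Planned withdrawal is the result the treatment aims for; stopping after failure is the reverse; stopping for toxicity says little about disease control. Because the event is unqualified and the list of competing events is closed, all three score alike unless death or transplant comes first. A higher incidence in one arm could then reflect more successful weaning, more failure, or a mixture.

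The protocol already has what is needed to separate them. Sections 9.6.2 to 9.6.4 treat any new AA treatment and clonal evolution as competing events for the response endpoints, and 9.2 ties CsA independence to the absence of relapse. Section 9.6.8 uses neither. What is at stake is the reading of a formally tested secondary endpoint, and any statement drawn from it about whether eltrombopag helps patients come off CsA.

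**Working it through.** **Plan's own figure.** The protocol states no expected rate for this endpoint, so there is nothing to reproduce. The only design figure, 96 per arm for 7% v 21%, is reproduced by the pooled-variance formula (two-sided 5%, 80% power) and does not bear on this point.

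**Timing (8.12, 9.4, 7.2.3).** Tapering from month 12 at 10% per month ends at month 12 + 10 = 22, with a floor of 18 months on CsA. Follow-up is 24 months. Planned withdrawals therefore fall in months 18 to 24. Treatment failure can be declared at month 6, so stops after failure can occur up to a year before the first planned withdrawal. Any event before month 18 is not a planned withdrawal, yet it counts as one.

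**Direction.** Notation, for each arm:
- r = share responding
- w = share of responders weaned by month 24
- s = share of non-responders who stop CsA with no earlier death or transplant

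Use the same w and s in both arms, and ignore relapse after response for simplicity. Then:
- incidence of the endpoint = r·w + (1 − r)·s
- incidence of weaning = r·w
- endpoint difference = [rE·w + (1 − rE)·s] − [rC·w + (1 − rC)·s] = (rE − rC)(w − s)
- weaning difference = (rE − rC)·w

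The ratio of the two differences is 1 − s/w: diluted for 0 < s < w, zero at s = w, reversed for s > w.

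**Numbers.** rC = 0.68 is the 6-month response on horse ATG plus CsA quoted in section 2. Assumptions not in the documents: rE = 0.80, w = 0.2 to 0.6, s = 0 to 0.8. So rE − rC = 0.12.

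| w | s | Endpoint, control v eltrombopag | Difference | Weaning, control v eltrombopag | Difference |
|---|---|---|---|---|---|
| 0.4 | 0 | 27.2% v 32.0% | +4.8 | 27.2% v 32.0% | +4.8 |
| 0.4 | 0.2 | 33.6% v 36.0% | +2.4 | 27.2% v 32.0% | +4.8 |
| 0.4 | 0.4 | 40.0% v 40.0% | 0 | 27.2% v 32.0% | +4.8 |
| 0.4 | 0.8 | 52.8% v 48.0% | −4.8 | 27.2% v 32.0% | +4.8 |
| 0.2 | 0.8 | 39.2% v 32.0% | −7.2 | 13.6% v 16.0% | +2.4 |
| 0.6 | 0.25 | 48.8% v 53.0% | +4.2 | 40.8% v 48.0% | +7.2 |

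Example, fourth row: control 0.68 × 0.4 + 0.32 × 0.8 = 0.272 + 0.256 = 0.528; eltrombopag 0.80 × 0.4 + 0.20 × 0.8 = 0.320 + 0.160 = 0.480.

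**Toxicity in responders.** If a further share t of responders stop for toxicity, the endpoint difference becomes (rE − rC)(w + t − s). With w = 0.4, t = 0.05 and s = 0 it is 30.6% v 36.0%, or +5.4 against a planned-weaning difference of +4.8. These stops push the other way, by a small amount.

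**The case against.** **All-cause stopping may be what was meant.** Objective 10 speaks only of discontinuation, successful weaning has its own endpoint (number 11, CsA-independent response at 24 months), and an all-cause curve beside a success rate is a legitimate pair. This stands in part, and it is why all-cause stopping should stay as a description. But endpoint 11 is only summarised by frequencies at one time point (9.6.10, 12.3), while the mixed endpoint is the one formally tested over time.

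**The detail may belong to the SAP, or be implied by the word maintenance in the synopsis.** The SAP could add the reason for stopping. But 9.6.8 already fixes the competing events, and the word is undefined and absent from 5.2 and 9.6.8. It remains true that no sentence says outright that stops for failure or toxicity count; that follows from the open event and the closed list.

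**s may be small.** A patient moved to a second immunosuppressive course has arguably not discontinued immunosuppression, and transplant, which 8.11 says should be considered for non-responders, already competes. Both points lower s, and reversal needs s above w. This stands: reversal is possible, not established, and it would be too strong to say that the endpoint has no interpretable direction.

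**A stronger reading that the text does not support.** Because 8.11.1 offers open-label eltrombopag as "Single agent treatment" to control-arm non-responders only, a reader might infer that the mix of reasons differs by arm by design. The section does not say that CsA is stopped in these patients, and non-responders in both arms may receive second-line treatment chosen by the investigator. The arithmetic above does not need this asymmetry; a difference in response rate is enough.

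**Conclusion.** The defect holds as a matter of definition. Section 9.6.8 merges withdrawal in stable response with stopping after failure or for toxicity, and 12.3 tests the merged event. With equal stopping behaviour in both arms, the weaning difference is multiplied by 1 − s/w. Under the assumed rates, a true +4.8 points can appear as anything from +4.8 to −4.8 as s runs from 0 to 80% with w = 40%. Only the 68% is a document figure, and it comes from an earlier trial; rE, w and s are assumptions, so the table shows what can happen and is not a forecast. The Gray test and Cox result can therefore mislead about weaning, but they need not.

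This is one of 15 secondary endpoints. The primary endpoint and sample size are unaffected, and CsA-independent response at 24 months is still reported. The change is worth making, but it does not threaten the trial's main conclusion.

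**What to change.** In 9.6.8:
- **Event:** CsA discontinued while in CR or PR, without relapse or new AA treatment, whatever the reason for stopping. This matches 9.2, which asks for dose reduction without relapse and not for a reason, and it avoids classing a responder stopped for toxicity as both event and competing event.
- **Competing events:** death, SCT, relapse, any new specific AA treatment, clonal evolution, and CsA stopped while not in response. This follows the list in 9.6.2.
- **Descriptive report:** all-cause discontinuation by arm, split by reason.

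Bring the wording in 1.1, 4.2 and 5.2 into line. The change concerns the endpoint definition only and leaves patient management as it is.

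Cost: a few sentences. The reason for stopping and the response status at stopping must be available from the CRF, which is not shown, so this needs checking. The tested event also becomes rarer (27.2% instead of 40.0% in control at s = w = 40%), so the comparison has fewer events to work with.
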